7.2.1 Nomenclature/description

Terminology used to describe an adverse event is very important. Preferred terms to be used to describe any observed/identified AE(s) are defined as in the abridged version of the **NCI Common Terminology Criteria for Adverse Events (NCI-CTCAE) version 5** (38) (Appendix xix). The preferred terms are descriptive terminology which should be utilized for AE reporting in the CRF. A grading (severity) scale is also provided for each AE term. Inaccurate or inconsistent coding of events may lead to missed safety signals.

7.2.2 Severity (Grade)

Grade refers to the severity of the AE. The study abridged version of **NCI CTCAE** displays Grades 1 -5 with unique clinical descriptions of severity for each AE

Table 4: Adverse effects grading with unique clinical descriptions of severity

Severity	Definition
Grade 1	Mild; asymptomatic or mild symptoms; clinical or diagnostic observations only; intervention not indicated.
Grade 2	Moderate; minimal, local, or non-invasive intervention indicated; limiting age-appropriate instrumental ADL*
Grade 3	Severe or medically significant but not immediately life-threatening; hospitalization or prolongation of hospitalization indicated; disabling; limiting self-care ADL**.
Grade 4	Life-threatening consequences: urgent intervention indicated
Grade 5	Related to death

Activities of Daily Living (ADL)

^{*}Instrumental ADL refer to preparing meals, shopping for groceries or clothes, using the telephone, managing money, etc.

^{**}Self-care ADL refer to bathing, dressing, and undressing, feeding self, using the toilet, taking medications, and not bedridden.

7.2.3 Relationship of AE to study product

The Chief Investigator or designated Principal Investigator must determine the relationship of the AE to the product under investigation and document in the appropriate section of the e-CRF. For each AE, an assessment of the relatedness to the study drugs should be made using the following scale:

- **Unrelated:** Onset of the AE had no reasonable temporal relationship to administration of the study product or a causal relationship to administration of the study product is biologically implausible or the event is attributed to an alternative etiology.
- **Unlikely-related**: Onset of the AE has an inconceivable possibility that the event was related to, or caused by the investigational intervention?
- **Possibly related:** Onset of the AE has a reasonable temporal relationship to study product administration and a causal relationship is not biologically implausible.
- **Probably related:** Onset of the AE has a strong temporal relationship to administration of the study product that cannot be explained by the participant's clinical state or other factors and a causal relationship is not biologically implausible.
- **Definitely related:** Onset of the AE shows a distinct temporal relationship to administration of the study product that cannot be explained by the participant's clinical state or other factors, or the AE occurs on re-challenge, or the AE is a known reaction to the product or chemical group or can be predicted by the product's pharmacology.
- These criteria in addition to good clinical judgement should be used as a guide for determining the causal assessment. If it is felt that the event is not related to study drug therapy, then an alternative explanation should be provided.

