- p) Incidence of post-natal maternal death from enrolment up to six weeks and at six months postpartum.
- q) Incidence of adverse drug events.
- r) Quality of life measured using the WHOQOL BREF at enrollment, six weeks, and six months post-partum.

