7.3.2.2 Gastro-intestinal disorders

Abdominal discomfort and anorexia, abdominal pain, nausea, and vomiting (these are usually dose related), constipation, diarrhea, and dark stools. Contact irritation can occur with ferrous sulphate tablets resulting in erosion or ulceration, particularly if they become lodged in the upper gastrointestinal tract.

Caution:

- Ask patients to keep medication out of the sight and reach of children, as overdose may be fatal.
- Ask about previous allergy to iron formulations.
- Administer oral FS with caution in patients with existing gastrointestinal disease like difficulty in swallowing and inflammatory bowel diseases.
- Due to the risk of mouth ulcerations and tooth discoloration, tablets should not be sucked, chewed, or kept in the mouth but swallowed whole with water.
- Advise to take FS 1 hour before meals or 2 hours after meals with a full glass of water

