7.4 Data analysis plan for adverse events (Harm)

Using intention to treat analysis, the absolute risk, the frequency/incident rate and severity grade of anticipated adverse drug reactions such as abdominal pain, nausea and vomiting, hypotension and hypophosphatemia for participants in each study arm, the incident rate of any Serious Adverse Reactions (SAR) which are SAEs that are thought to be causally linked to the trial drug and Suspected Unexpected Serious Adverse Reaction (SUSAR) which are unexpected occurrence of a SAR for each arm of the study will be collated and analyzed. The mean and SDs or median and interquartile range for serum phosphate level will be calculated as appropriate, while extreme values will be stated if observed.

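### In 7.2.3 the re-challenge and known-reaction routes to 'Definitely related' carry no timing or alternative-cause condition, so one post-dose event can also be 'Unrelated', with no tie-break

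*Protocol*

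**What the plan says.** Protocol 7.2.3 asks the Chief Investigator or a designated Principal Investigator to place each adverse event on a five-step scale.

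- *Unrelated* is met by any one of three alternatives. The first is "Onset of the AE had no reasonable temporal relationship to administration of the study product", the second is a biologically implausible link, and the third is "or the event is attributed to an alternative etiology".
- *Unlikely-related* is worded "Onset of the AE has an inconceivable possibility that the event was related to", or was caused by, the intervention. The sentence ends in a question mark.
- *Possibly related* needs a reasonable temporal relationship and a link that is not implausible. *Probably related* needs a strong temporal relationship that the participant's condition or other factors do not explain, again with a link that is not implausible.
- *Definitely related* opens with "Onset of the AE shows a distinct temporal relationship to administration of the study product that cannot be explained by the participant's clinical state"; explanation by anything else is ruled out in the same way. It then adds, each joined by an 'or', recurrence on re-challenge and finally "or the AE is a known reaction to the product or chemical group or can be predicted by the product's pharmacology".

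The section closes by calling the criteria a guide alongside clinical judgement. It asks for another explanation when an event is felt not to be related. Section 7.2 fixes events before the first dose as not related.

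The ratings are relevant to two places. Section 7.4 reports serious adverse reactions, "which are SAEs that are thought to be causally linked to the trial drug". Section 3.1.2 (q) lists "Incidence of adverse drug events" as a secondary outcome without naming a relatedness grade.

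**The concern.** A causality scale should rise in one direction, and each event should fall in one grade. This one fails on three counts.

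1. The two extreme grades overlap. The timing and no-other-explanation conditions belong only to the first alternative of *Definitely related*. A known reaction, or recurrence on re-challenge, suffices alone, even where timing or another cause satisfies *Unrelated*.
2. The order inverts. The two middle grades need a temporal relationship, but the top grade can be reached without one.
3. The two lowest grades are reversed in strength. An inconceivable link is a stronger denial than the absence of a reasonable temporal relationship.

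What is at stake is the consistency of every count that depends on relatedness. Section 4.1 gives each of the four states its own Principal Investigator, and 7.2 assigns causality to the principal investigator, so several people may apply the scale. The blinding in 4.5 covers the research nurse who collects subjective outcomes; none is stated for the causality rater in this open-label trial. Two raters could follow the text and record opposite answers for the same event.

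**Working it through.** The protocol gives no adverse drug event rate, so there is no figure to reproduce. The check is one of logic.

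**A worked case.** A woman in the oral arm vomits at the 12-week visit and has confirmed malaria. Scheduled tablets run to six weeks (4.6.1), adverse events are collected to the end of the study (7.2), and malaria is tested whenever symptoms suggest it (4.9). Assume she has taken no iron since week six.

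| Definition in 7.2.3 | Met? | Why |
|---|---|---|
| *Unrelated* | Yes | Last tablet six weeks earlier; malaria explains it |
| *Definitely related* | Yes | Vomiting is listed for ferrous sulphate in 7.3.2.2: "Abdominal discomfort and anorexia, abdominal pain, nausea, and vomiting (these are usually dose related), constipation, diarrhea, and dark stools" |
| *Possibly* or *Probably related* | No | Both need a temporal relationship |

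**All combinations.** Take five yes/no facts: T (timing fits), I (link implausible), A (alternative cause), K (known or predictable reaction), R (recurs on re-challenge). As a simplification, reasonable and distinct timing are one fact, and not being explained by clinical state or other factors is taken as no A. There are 2^5 = 32 combinations.

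- *Unrelated* = not T, or I, or A. It fails only when T holds and I and A do not: 4 combinations. So 32 − 4 = 28 meet it.
- *Definitely related* = (T and not A), or R, or K. K or R holds in 24 combinations. With neither, T and not A adds 2. So 24 + 2 = 26 meet it.
- No combination meets neither, because the 4 that fail *Unrelated* all have T without A. Both are met in 28 + 26 − 32 = **22 of 32**.

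The 22 divide as follows:

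- K without R: 7
- R without K: 7
- both K and R: 7
- neither: 1, an implausible link with good timing and no other cause, because even the first alternative lacks a plausibility condition.

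These are combinations of facts, not frequencies of events.

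**After the change.** If T and not A is required for every *Definitely related* rating, an overlap needs T, not A and I, with K and R free: 2 × 2 = 4 combinations. Capping implausible links at *Unlikely* removes those 4, leaving 0.

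**Can a direction be shown?** All rates here are assumed. Let b be the background rate of gastrointestinal symptoms in both arms and d the drug-caused rate, 10% oral and 2% intravenous (true difference 8 points). If every listed symptom counts, the rate is 1 − (1 − b)(1 − d).

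| b | Oral | Difference if only oral is affected | Intravenous, if 'chemical group' means iron | Difference then |
|---|---|---|---|---|
| 5% | 14.5% | 14.5 − 2 = 12.5 points | 6.9% | 7.6 points |
| 10% | 19.0% | 19.0 − 2 = 17.0 points | 11.8% | 7.2 points |
| 20% | 28.0% | 28.0 − 2 = 26.0 points | 21.6% | 6.4 points |

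One reading widens the contrast and the other narrows it slightly. With d = 5% in both arms, the second reading leaves a difference of 0.

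**The case against.** The strongest reply is that 7.2.3 does not bind the rater. The criteria guide clinical judgement, and a rater may record the malaria case as not related and name malaria. Section 7.2 also settles pre-dose events. This stands as far as it goes: nothing is attributed automatically, and the problem is confined to post-dose events. But judgement is not told which definition prevails when both are met, so opposite ratings remain defensible.

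A second reply is that little depends on the scale. Section 7.4 lists anticipated reactions by type and arm and names no relatedness grade, and outcome (q) names no cut-off. For suspected unexpected serious reactions, 7.2.6 requires an event outside the product information and only a reasonable possibility of causation, so the known-reaction alternative has little bearing there. This largely stands. It narrows the exposure to serious adverse reactions, and to adverse drug events if these are defined by relatedness.

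A reader might go further and infer that adverse drug event rates are inflated, mainly for oral iron, because 7.3.2.2 lists common gastrointestinal symptoms while 7.3.1 lists only hypersensitivity and extravasation for ferric carboxymaltose. About 20 of 26 weeks (77%) of collection follows the last scheduled tablet. With an assumed background of 3 to 10%, that suggests 0.03 × 700 = 21 to 0.10 × 700 = 70 women, or 3 to 10 points. The documents do not support this:

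- The background rates have no source in the protocol. The figure needs every such event rated *Definitely related* in the oral arm and none in the intravenous arm.
- The clause extends to the chemical group, which can bring the same symptoms into the intravenous arm.
- Section 1.1 reports reduced serum phosphate with ferric carboxymaltose, and phosphate is measured at two and six weeks, so 7.3.1 is not the full list of its known reactions.
- After a single infusion nearly all follow-up is remote from dosing, so the missing timing condition may matter more in that arm.
- The 77% is calendar time, and note b to Table 2 allows oral iron after week six in women still below 11 g/dl.

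**Conclusion.** The scale contradicts itself as written and should be corrected. For post-dose events, *Unrelated* and *Definitely related* overlap without a tie-break in 22 of 32 combinations of facts. The top grade can be reached with less than the two grades below it require, and *Unlikely-related* is worded more strongly than *Unrelated*. This rests on a literal reading and on the two simplifications stated with the count.

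The consequence is possible misclassification of relatedness-based counts, with size and direction uncertain. A finding of inflated rates or of bias against oral iron is not established. The primary outcome, hemoglobin at six weeks, is unaffected.

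**What to change.** Revise the definitions in 7.2.3 and the matching e-CRF help text:

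1. **Cap.** An event with no reasonable temporal relationship, a biologically implausible link or a confirmed alternative cause cannot be rated above *Unlikely*.
2. **Definitely related.** Every rating needs a distinct temporal relationship that clinical state or other factors do not explain. Re-challenge, or a known or predictable reaction, is supporting evidence: not sufficient alone, and not required for a new reaction. Making it required would keep a previously unknown reaction to single-dose ferric carboxymaltose out of the top grade, since no re-challenge is planned.
3. **Unlikely-related.** Define it as a causal link that is improbable but not excluded. Keep *Unrelated* for a link that is excluded, and tighten its three alternatives to match, so that another cause which only makes the drug less likely leads to *Unlikely*.

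The cost is one block of definitions, the help text and a short note to raters. The downside is small: events already rated need a re-check against the new wording.

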7.2.4 Duration of AE

Start and Stop date of AE must be reported in the e-forms. This may be unknown or ongoing even at final physical examination. The study clinician must make effort to document the best estimates of duration of AE or if it is still ongoing

7.2.5 Serious Adverse Events

A Serious Adverse Event (SAE) is defined as an event which:

- > is fatal or life-threatening
- results in persistent or significant disability/incapacity
- constitutes a congenital anomaly/birth defect
- requires inpatient hospitalization or prolongation of existing hospitalization, unless hospitalization is for:
 - o routine treatment or monitoring of the studied indication, not associated with any deterioration in condition.
 - o elective or pre-planned treatment for a pre-existing condition that is unrelated to the indication under study and has not worsened since the start of study drug.

- o treatment on an emergency outpatient basis for an event not fulfilling any of the definitions of a SAE given above and not resulting in hospital admission.
- o social reasons and respite care in the absence of any deterioration in the patient's general condition.
- is medically significant, i.e., defined as an event that jeopardizes the patient or may require medical or surgical intervention to prevent one of the outcomes listed above

Note: Unlike routine safety assessments, SAEs are monitored continuously and have special reporting requirements as shown below.

7.2.6 Suspected Unexpected Serious Adverse Reactions (SUSARs)

A Suspected Unexpected Serious Adverse Reaction (SUSAR) is defined as an untoward and unintended response to a study drug, which is not listed is the product information, and meets one of the following serious criteria: results in death, is life-threatening, requires hospitalization or prolongation of an existing hospitalization, results in persistent or significant disability or incapacity, or is a congenital anomaly or birth defect. Investigators will determine whether an AE is a SUSAR given the participants clinical course, previous medical conditions, and concomitant medications. SUSARs are assessed by the sponsor and or study investigator as being unexpected, serious, and as having a reasonable possibility of a causal relationship with the study drug. Reports of these reactions are subject to expedited submission to health regulatory authorities.

Reporting SAEs and SUSARs

- All SAEs and SUSARs must be reported by the site clinician to the Principal Investigator and in turn to Chief Investigator as soon as possible after the SAE or SUSAR is identified.
- ➤ Site clinician must report SAEs and SUSARs to the PI who should report to the CI within 24 hours of the study site becoming aware of the problem. The investigator may report the SAE via telephone or email; however, a SAE report form must be completed as soon as possible after the informal report.
- The *Principal Investigator* will complete *SAE report form (Appendix xx)* and forward to the CI for reporting to the Steering committee (TSC), DSMC and using the pharmacovigilance form (*Appendix* xxi) to NAFDAC.
- ➤ A SUSAR that meets the seriousness criteria of life-threatening and/or results in death must be reported by the CI to the TSC within seven (7) calendar days. A SUSAR that is not life-threatening or does not result in death must be submitted to the regulatory authorities within fifteen (15) calendar days.

7.2.7 Treatment of adverse events

All adverse events should be treated appropriately. Treatment may include one or more of the following:

- No action taken (i.e., further observation only).
- Study drug dosage adjusted/temporarily interrupted.
- Study drug permanently discontinued due to this adverse event.
- Concomitant medication given.
- Non-drug therapy given.
- Patient hospitalized/patient's hospitalization prolonged.

The action taken to treat the adverse event should be recorded on the adverse event e-CRF.

- Once an adverse event is detected, it should be followed up until its resolution or until it is judged to be permanent, and assessment should be made at each visit (or more frequently, if necessary) of any changes in severity, the suspected relationship to the study drug, the interventions required to treat it, and the outcome.
- Information about common side effects already known about the investigational drug will be included in the patient informed consent and should be discussed with the patient during the study as needed.

7.2.8 Outcome of SAEs

The outcome of a SAE should be reported as follows:

- Resolved
- Ongoing
- Resolved with minor sequelae
- Resolved with major sequelae

This reporting is required in the end of study form.

7.3 Safety

Adverse events will be monitored throughout the study to assess the general safety and tolerability of the two treatment groups.

Safety assessments will consist of:

- monitoring and recording all adverse events
- the monitoring of laboratory tests results
- regular measurement of vital signs
- physical examinations as indicated.

7.3.1 Safety issues with ferric carboxymaltose

7.3.1.1 Hypersensitivity reactions (HSRs)

Parenterally administered iron preparations including FCM can cause hypersensitivity reactions including serious and potentially fatal anaphylactic/anaphylactoid reactions (39). The risk is enhanced for patients with known allergies including druq allergies, patients with a history of severe asthma, eczema, or other atopic allergies. There is also an increased risk of hypersensitivity reactions in patients with immune or inflammatory conditions (e.g., systemic lupus erythematosus, rheumatoid arthritis). **These conditions with increased risk for HSRs are excluded from this study.**

Other risk factors for hypersensitivity reaction are previous reaction to intravenous iron, fast iron infusion rate and staff or patient anxiety.

- FCM should only be administered when study staff that are trained to evaluate and manage anaphylactic reactions are immediately available and, in an environment, where full resuscitation facilities can be assured.
- Each patient should be observed for adverse effects for at least 30 minutes following FCM administration. If hypersensitivity reactions or signs of intolerance occur during administration, the infusion must be stopped immediately, and the resuscitation protocol activated (*Refer to IVON Trial Protocol No: 02; Administration of Intravenous Ferric Carboxymaltose and the Emergency Treatment of Hypersensitivity Reaction Type 1 (Anaphylaxis).*
- Facilities for cardiorespiratory resuscitation and equipment for handling acute anaphylactic/anaphylactoid reactions should be available, including an injectable 1:1000 adrenaline solution. Additional treatment with antihistamines and/or corticosteroids should be given as appropriate.

CAUTION:

- Acute hypersensitivity reactions during iron infusions are very rare but can be life-threatening and so these special precautions must be always considered.
- Every administration of FCM:
 - Must be preceded by a recheck for risk factors for an HSR, the general condition of the patient and base-line observations including pulse rate, blood pressure and respiratory rate.
 - The infusion should be prepared as stated in the manufacturer's instructions.
 - Infusion should be initiated slowly and not increased until it is clear that it is being welltolerated (usually after 5-10 min).
 - Observation/monitoring every 15 min and for 30 min after the infusion finishes.
 - A test dose is not appropriate or necessary as it may give false reassurance.
 - Patients should be closely monitored for signs of hypersensitivity during and for at least 30 min after administration.

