4.2.1 Selection of participants

Inclusion criteria:

- a) Women aged between 15 and 49 years.
- b) Between six and 48 hours after delivery. A minimum of six hours has been chosen because we expect the initial post-birth blood loss to have subsided and the hemoglobin concentration to be sufficiently representative of the true hemoglobin concentration at that time; 48 hours has been chosen as the upper limit for pragmatic reasons because women are usually discharged from hospital after 48 hours.
- c) Baseline (enrollment) moderate or severe anemia (**Hb≤9.9g/dl**), confirmed by Hemocue haemoglobinometer.
- d) Able and willing to give written informed consent.

Exclusion criteria:

- a) Having received a blood transfusion, for any indication, within the last three months.
- b) Symptomatic anemia and a need for urgent correction.
- c) Known haemoglobinopathy such as sickle cell disease, HbCC disease.
- d) Clinically confirmed malabsorption syndrome.
- e) Known hypersensitivity or contraindication to any form of iron treatment, study drug or any of its excipients.
- f) Self-reported pre-existing maternal depression or other psychiatric illness and as evidenced by a YES response to Any Past history of Psychiatry ward hospitalization, Psychiatry medications, behavioral changes, or past consultation with Psychiatry services.
- g) Severe allergic conditions such as severe asthma, eczema, or other atopic condition.
- h) Known autoimmune conditions e.g., systemic lupus erythematosus, rheumatoid arthritis or known severe drug allergies.
- i) Planning to move or reside outside the research area
- i) Women who have had intravenous iron administered in the last two years (26).

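### Section 7.3.1.1 states that women with known allergies are excluded because of hypersensitivity risk, but section 4.2.1 excludes drug and other allergies only when they are severe

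*Protocol*

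**What the plan says.** Section 7.3.1.1 describes who is at higher risk of a hypersensitivity reaction to FCM. One sentence begins "The risk is enhanced for patients with known allergies including" and goes on to name drug allergies, then a history of severe asthma, eczema or other atopic allergies. The next begins "There is also an increased risk of hypersensitivity reactions in patients with" and refers to immune or inflammatory conditions, with lupus and rheumatoid arthritis as examples. The protocol then states in bold: "These conditions with increased risk for HSRs are excluded from this study". Further factors follow that statement: "Other risk factors for hypersensitivity reaction are previous reaction to intravenous iron", a fast infusion and anxiety.

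Section 4.2.1 holds the operative exclusion criteria. Criterion (g) reads "Severe allergic conditions such as severe asthma, eczema, or other atopic condition". Criterion (h) covers known autoimmune conditions and ends "rheumatoid arthritis or known severe drug allergies". Criterion (e) covers known hypersensitivity or contraindication to any iron treatment, the study drug or its excipients.

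The caution list in section 7.3.1.1 adds that every FCM administration "Must be preceded by a recheck for risk factors for an HSR". Section 4.10.2 places randomisation first among the visit 1 steps and study drug administration last. Section 9.3 defines the intention-to-treat set so that a woman must have had at least one dose of study drug.

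**The concern.** The exclusion statement sits in the section on reactions that the protocol itself calls potentially fatal. It tells sites, monitors and ethics committees that a named risk has been removed by eligibility. If the criteria do not remove it, the stated safeguard does not exist for some women who will be infused.

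The mismatch also makes compliance ambiguous. Section 11.1 lists inclusion and exclusion errors as protocol violations. A monitor working from section 7.3.1.1 and one working from section 4.2.1 could classify the same woman differently, and there are 20 sites.

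There is a possible statistical consequence. If the wider wording first takes effect at the pre-infusion recheck, it does so after allocation and in one arm.

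**Working it through.** The point rests on text, and the protocol states no figure for it that could be reproduced. The two lists compare as follows.

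| Condition | Section 7.3.1.1 (said to be excluded) | Section 4.2.1 (actual criterion) | Match? |
|---|---|---|---|
| Drug allergy | Any known | Severe only, (h) | No |
| Other known allergy | Any known | Severe allergic conditions only, (g) | No |
| Severe asthma | Yes | Yes, (g) | Yes |
| Eczema, other atopy | Listed after severe asthma | Listed after severe asthma, under a heading of severe conditions, (g) | Unclear |
| Autoimmune conditions | Yes, as immune conditions | Any known, no severity limit, (h) | Yes |
| Inflammatory, not autoimmune | Yes, by its wording | No criterion names them | Unclear |

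**Step 1: the direct contradiction.** The first two rows need little interpretation. Section 7.3.1.1 sets no severity limit on known allergies and section 4.2.1 does. A woman with a non-severe drug allergy is therefore both excluded (7.3.1.1) and eligible (4.2.1). Section 4.10.1 screens against the eligibility criteria, so in practice she is enrolled.

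**Step 2: the unclear rows.** For eczema and other atopy, the word severe may govern only asthma or the whole phrase, in either section. For inflammatory conditions, both examples in section 7.3.1.1 are also named in criterion (h), so the intended scope may be the same, but the words are wider.

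**Step 3: the possible route to unequal loss.**
1. Section 4.10.2 randomises before study drug is given.
2. The hypersensitivity recheck is written for FCM only. For ferrous sulphate (FS), section 7.3.2.2 has only a question about earlier allergy to iron formulations.
3. A clinician who finds a drug allergy at the recheck, and has read that such women are excluded, has a reason to withhold FCM.
4. A woman who is never dosed fails the section 9.3 definition of the intention-to-treat set. A similar woman in the FS arm would receive her tablets and could stay in it.

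The protocol does not state what follows a positive recheck, so item 3 is an inference.

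**Step 4: scale, with assumed rates only.** Each 1% of women with a qualifying allergy is 0.01 × 1,400 = 14 women, about 7 per arm. If a share u of the 700 FCM women were not infused, stayed in the analysis and had the control anemia rate, the FCM rate would be 0.30 + u × (0.39 − 0.30). With 700 × 0.9 = 630 evaluable per arm and two-sided alpha 0.0492, a normal approximation for two proportions, with pooled variance under the null, gives:

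| u (assumed) | FCM women not infused | FCM anemia rate | Power |
|---|---|---|---|
| 0 | 0 | 0.3000 | 91.9% |
| 1% | 7 | 0.3009 | 91.4% |
| 2% | 14 | 0.3018 | 90.8% |
| 5% | 35 | 0.3045 | 89.0% |
| 10% | 70 | 0.3090 | 85.4% |

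Power is therefore not the main issue at small u. This table does not measure the selection effect in step 3, where women leave the analysis set. The documents give nothing from which to size that.

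**The case against.** The best case for the protocol is that section 4.2.1 is operative and section 7.3.1.1 is descriptive, so a loose sentence in the latter changes nobody's eligibility. Every FCM recipient also has trained staff, resuscitation facilities and at least 30 minutes of observation. That limits the harm from the mismatch, but the sentence still reports a safeguard that the criteria do not provide.

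Several stronger readings are tempting and do not hold:

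- **That all hypersensitivity risk factors are said to be excluded.** The statement covers the conditions named before it. Earlier reaction to intravenous iron, fast infusion and anxiety come after it.
- **That section 4.2.1 removes only severe forms throughout.** Known autoimmune conditions (h) and known hypersensitivity to iron, study drug or excipients (e) are excluded at any severity, and severe asthma matches.
- **That mild atopy is plainly contradicted.** The atopy phrases in the two sections are nearly identical and can be read the same way. The defect there is ambiguity.
- **That section 7.3.2.2 shows women with inflammatory bowel disease are enrolled.** It says "Administer oral FS with caution in patients with existing gastrointestinal disease like difficulty in swallowing and inflammatory bowel diseases", but the same list tells staff to ask about earlier allergy to iron formulations, although criterion (e) already excludes women with known hypersensitivity to iron. A caution there does not show who is enrolled.
- **That women will be stopped after randomisation in the FCM arm only.** No action after a positive recheck is stated. The discontinuation rule in section 6.5 covers both arms and needs approval from the chief or principal investigator. FCM administration is also governed by a separate document that is not at hand.

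Section 4.10.1 already assesses eligibility before randomisation, so the structure for the remedy exists. The two lists still differ.

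**Conclusion.** The protocol contradicts itself on drug allergies and other known allergies. Section 7.3.1.1 says these women are excluded at any severity; section 4.2.1 excludes them only when the allergy is severe. The safeguard stated in the safety section is therefore not delivered by the eligibility criteria. Eczema, other atopy and non-autoimmune inflammatory conditions are unclear rather than contradictory.

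The number of women concerned cannot be derived from the documents. One-sided withholding after randomisation, and loss from the intention-to-treat set through its one-dose requirement, is a foreseeable consequence and not a written rule. It depends on the assumption that some clinicians act on the wider wording at the recheck. The conclusion does not depend on power. The change should be made because it is cheap and corrects a statement about potentially fatal reactions.

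**What to change.** Reconcile criteria (g) and (h) of section 4.2.1 with section 7.3.1.1 into one list of hypersensitivity exclusions, worded identically in both places, with the severity term attached explicitly to each item. Which conditions and severities belong on it is for the sponsor and safety board to decide. Complete that list for every woman at screening, before randomisation, so that the pre-infusion recheck only catches new information.

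The cost is a protocol wording change and, if the screening log does not already carry these items, an edit to that form. If the wider wording is chosen, somewhat fewer women will be eligible; how many is unknown. If the narrower wording is chosen, the exclusion statement in section 7.3.1.1 must be cut back to match.
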